7. STATISTICAL METHODS AND DETERMINATION OF SAMPLE SIZE

This trial is designed as a randomised, parallel-group, double-blind, and placebo-controlled trial with 4 active doses of BI 655130 in patients with moderate to severe Palmoplantar Pustulosis.

The purpose of this trial is to demonstrate proof of concept of clinical activity of BI 655130 on the primary endpoint of % PPP ASI change at Week 16. For the proof of concept a combined criterion of MCPMod testing (with respect to achieving a non-flat dose response curve) and evaluation of a minimum relevant benefit is implemented. In detail, for PoC, at first a statistically significant non-flat dose-response needs to be detected. For this purpose, a multiple comparison procedure with modelling techniques (MCPMod) approach is applied. Subsequently, at least one dose should show a benefit of at least 20% compared to placebo (i.e. the maximum benefit of BI 655130 for achieving the primary endpoint, based on modelled dose-response curve using model averaging across the statistically significant models (see [Section 7.2.2](#)), shows a $\geq 20\%$ larger reduction compared to placebo).

Overall this approach is applied to define suitable dose regimens for BI 655130 regarding efficacy and safety for further pivotal testing in a subsequent study. Further assessment on the efficacy of BI 655130 at time-points after Week 16 will be performed in an exploratory manner.

Baseline refers to the measurement recorded at randomisation (Visit 2); if data at Visit 2 is missing, then data from Visit 1 will be considered baseline. The percent change from baseline of the PPP ASI score, at all follow-up visits (X), is calculated as:

$$\% \text{ PPP ASI change from baseline} = \frac{(\text{PPP ASI at Visit X} - \text{PPP ASI at baseline})}{\text{PPP ASI at baseline}} * 100.$$

For the derivation of the primary endpoint, all measurements collected after treatment discontinuation, or after the use of rescue therapy for the purpose of disease worsening, will be censored. The primary endpoint is then evaluated based on the results of a mixed effect model for repeated measurements (MMRM) which assumes that missing data up to Week 16 are handled via a missing at random approach. The estimated dose effects at Week 16 will then be analysed using the MCPMod approach techniques [[R10-1424](#), [R15-1961](#)].

Randomisation will be stratified, and analysis will be performed, based on a stratification according to Japan versus non-Japan.

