7.1 NULL AND ALTERNATIVE HYPOTHESES

The null hypothesis of the MCPMod test is that there is a flat dose response curve comparing the placebo and the BI 655130 dose groups on the primary endpoint of % PPP ASI change at Week 16. The alternative hypothesis is that there is a non-flat dose response curve indicating a (clinically relevant) benefit of BI 655130 over Placebo.

The MCPMod procedure allows for simultaneous evaluation of different potential dose response patterns, whilst protecting the overall probability of Type I error (one sided α of 5%). The pre-specified models and their parameters used for this test are outlined in [Section 7.2.2](#) and [Section 7.5](#).

Additionally, the probability of making a positive decision to continue the program with a non-effective drug is further limited by requesting that an effect of at least “delta” relative to placebo is achieved (see Section 7.5 for details). This consequently leads also to a reduction of the probability for having a false positive decision.

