7.5 DETERMINATION OF SAMPLE SIZE

Calculations were performed using R Version 3.5.1.

The study is intended to show a benefit of BI 655130 over placebo in terms of the difference in % PPP ASI change at Week 16.

The aims of this study are two-fold. A first aim is to show a significant non-flat dose-response curve across the different doses and placebo. Additionally to that at least one modelled dose within the dose range considered should show a benefit of at least "Delta" % PPP ASI change compared to placebo. The probability of success of this trial is therefore defined as the probability to (1) obtain a significant test for non-flat dose-response curve and (2) to observe for at least one of the modelled doses an effect difference of at least delta compared to placebo.

The sample size calculation is based on an assumed maximum difference in % PPP ASI change of placebo vs. BI 655130 of 30%, as well as on the pre-specified models listed in [Section 7.2.2](#). The standardized deviation of the % PPP ASI change is assumed to be 35%.

For placebo, a fixed rate of -25% PPP ASI change at Week 16 will be considered. These estimates are derived from trial 1368.15 in PPP.

Using a total sample size of 140 evaluable patients (40, 20, 20, 20 and 40 for placebo and low to high dose regimes respectively), the probability for a successful trial (as defined above) was estimated using simulations. For each dose group, samples of the required size were drawn from a normal distribution. Values smaller than -100% (which corresponds to complete recovery of a patient) were set to -100%. The expected values of the original normal distribution were chosen such that the expected dose group means after truncation correspond to the model assumptions. In the following, the reported dose means will always refer to dose means after truncation. The standard deviation of the untruncated normal distribution was set to 35% for all simulations. This will result in slightly reduced standard deviations after truncation (of approx. 30% for the highest dose group).

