Estimates for each dose group will be calculated and will be based on the final dose-response model. The choice of the target dose to be investigated in Phase 3 will be based upon efficacy as well as considering safety and other relevant information.

R code to perform the evaluations is available in [Section 9.4](#).

The following displays are planned.

- Table of the updated contrast coefficients per dose group and candidate model, together with the MCPMod test statistics and p-values for each model and the critical value
- For averaging model, figure of the dose-response curve
- For all significant model shapes, figures of the dose-response curve plus 95% confidence band (of the predicated shape) and 95% CI per dose (estimated from MMRM)
- For all significant model shapes, figure with the placebo corrected dose-response curve plus 95% confidence band (of the predicated shape).

R code is also available in [Section 9.4.1](#).

Descriptive statistics

Descriptive displays of percentage change from baseline in PPP ASI (with 95% CI) will be presented by treatment using OC and OC-IR methods respectively. The method to provide confidence intervals for each arm and unadjusted differences to placebo is derived from the Student's t-distribution.

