The estimate of response rate from each dose group obtained via logistic regression or penalized regression based on the Firth's bias reduction method (as described above) without intercept will be used as basis for the MCPMod analysis of the binary secondary endpoints. The subsequent MCP-Mod analyses are based on the response rates on the logit scale.

The multiple comparison procedure will be implemented using optimal contrast tests which control the family-wise type I error rate at a one-sided $\alpha = 0.05$. The same candidate models as for the primary endpoint will be used for all secondary binary endpoints. For the MCPMod test, the optimal contrasts of each candidate model are calculated using the R-function `optCont` using weights (w) proportional to the sample size of each dose group, respectively, and are shown in [Table 7.5.2: 1](#). These contrasts will be recalculated using the actual sample size of the dose groups (in case this differs from the planned numbers). The final contrasts will be presented in the CTR.

Table 7.5.2: 1 Contrast coefficient

Model	Contrast coefficients for (total) dose				
	Placebo	Low dose: [REDACTED]	Medium-low dose: [REDACTED]	Medium-high dose: [REDACTED]	High dose: [REDACTED]
Linear	-0.783	-0.049	0.049	0.196	0.587
E _{max}	-0.869	0.112	0.151	0.190	0.416
Exponential	-0.574	-0.194	-0.118	0.106	0.780
Logistic	-0.706	-0.220	0.036	0.279	0.612
Sigmoid E _{max}	-0.638	-0.247	-0.052	0.256	0.681

BI: Spesolimab total dose, [REDACTED] administered before week 16.

The MCP-Mod test will be applied using these fixed contrasts. R code is also available in [Section 9.4.2](#).

[figure not shown]
All significant dose-response models will be re-fitted to the data without any parameter assumptions to generate a set of new estimates of the model parameters from the data. The final model is derived as a weighted average over all significant model shapes obtained via the same averaging procedure as described for the primary endpoint.

The following displays are planned.

- Table of the contrast coefficients per dose group and candidate model, together with the MCPMod test statistics and p-values for each model and the critical value
- For the average model, figure of the dose-response curve
- For all significant model shapes, figures of the dose-response curve plus 95% confidence band (of the predicted shape)

Descriptive statistics

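### SAP 7.4 lists no interval for the model-averaged curve, and the single-model 95% bands, the only error bars on the placebo-corrected figures, can mislead at the low dose

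*SAP*

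**What the plan says.** Protocol Section 7 sets a two-part proof-of-concept rule: a significant non-flat dose response, and then "at least one dose should show a benefit of at least 20% compared to placebo", read from the curve averaged over the significant models. SAP 7.4 also takes the dose-response profile and the target dose from that average, and adds: "Estimates for each dose group will be calculated and will be based on the final dose-response model". No standard error or interval is mentioned for these estimates.

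The display list in SAP 7.4 treats the curves differently:

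- Averaged curve: "For averaging model, figure of the dose-response curve". No band is named.
- Each significant single model, uncorrected: curve, 95% band, and the MMRM 95% interval per dose.
- Each significant single model, placebo-corrected: "For all significant model shapes, figure with the placebo corrected dose-response curve plus 95% confidence band (of the predicated shape". No MMRM interval is named.

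SAP 7.5.2 repeats the pattern for the binary endpoints ("For the average model, figure of the dose-response curve"), again with bands only for single models.

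**The concern.** Models are averaged because the shape is unknown, yet each listed band treats one shape as known. The five candidate contrasts are similar enough that wrong shapes routinely pass the test and are displayed. A placebo-corrected figure can then show a narrow 95% band around a curve that is wrong at the lower doses, with no model-free interval beside it to expose the misfit.

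The trial is meant to define a dose range for Phase III. How precisely the lower regimens' effects versus placebo are known is part of that choice, and the estimate that carries the choice has no listed uncertainty.

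**Working it through.** **Inputs.** Protocol 7.5: "assumed maximum difference in % PPP ASI change of placebo vs. BI 655130 of 30" points; for placebo, "a fixed rate of -25% PPP ASI change at Week 16 will be considered"; SD 35 before values below -100% are set to -100%; n = 40/20/20/20/40. Protocol 7.1: "protecting the overall probability of Type I error (one sided α of 5"%. The absolute doses are not public, so relative doses are back-solved from the linear row of SAP Table 7.4: 2.

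**Relative doses.** Optimal contrasts are proportional to n_i × (d_i - d̄), up to sign. Placebo and high dose have equal n, so d̄ / (1 - d̄) = 0.783 / 0.587 and d̄ = 0.5715. For an arm of 20 the scale is 0.783 / 0.5715 / 2 = 0.685. Then:

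- low = 0.5715 - 0.049/0.685 = 0.500
- medium-low = 0.5715 + 0.049/0.685 = 0.643
- medium-high = 0.5715 + 0.196/0.685 = 0.858
- high = 1

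With these doses all five contrast rows of the table are recovered to three decimals.

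**Reproducing the plan.** Simulation of 10,000 trials per scenario, with AIC weights proportional to exp(-0.5 × AIC) and assumed parameter bounds. Success probability at delta 25:

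| Truth | Recomputed | Protocol Table 7.5: 1 |
|---|---|---|
| Linear | 75.4% | 77.1% |
| Emax | 80.3% | 80.7% |
| Logistic | 82.7% | 84.4% |
| Sigmoid Emax | 81.8% | 83.6% |
| Exponential | 75.6% | 79.0% |

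At delta 20 the linear scenario gives 92.3% against 93.2%. Only the exponential scenario is more than 2 points off.

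**Linear band at the low dose, by hand.**

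- Sum of n(d - d̄)² = 13.07 + 0.10 + 0.10 + 1.64 + 7.34 = 22.26.
- SE of the slope = 35/√22.26 = 7.42, so the SE of the effect at d = 0.5 is 3.71. Simulation gives about 3.5, because setting values to -100% lowers the SD.
- The fitted slope is Σ n(d - d̄)y / 22.26, with weights n(d - d̄) of -22.86, -1.43, 1.43, 5.73 and 17.14, and y the difference from placebo in Table 7.5: 1.
- For Emax, y = 0, -26, -27, -29, -30. The slope is (37.2 - 38.6 - 166.1 - 514.1)/22.26 = -30.6, so the fitted low-dose effect is -15.3 against a true -26, a bias of 10.7 points.
- Coverage ≈ Φ(1.96 - bias/SE) = Φ(1.96 - 10.7/3.71) = Φ(-0.92) = 18%.

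The same steps for the other shapes, beside the results of two simulation runs:

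| Truth | Fitted | True | Bias (absolute) | Coverage by hand | Simulated |
|---|---|---|---|---|---|
| Emax | -15.3 | -26 | 10.7 | 18% | 18-23% |
| Exponential | -13.9 | -4 | 9.9 | 24% | 21-23% |
| Logistic | -15.7 | -6 | 9.7 | 26% | 22-26% |
| Sigmoid Emax | -15.2 | -3 | 12.2 | 9% | 7-9% |

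When the truth is linear, the band covers 95%.

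**Other single-model bands** (trials with a significant test, effect versus placebo):

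| Dose | Band | Coverage |
|---|---|---|
| Low | Best AIC | 90% (linear truth); 49-61% (other truths) |
| Low | Emax | 98-99% (linear or Emax truth); 53-74% (other truths) |
| Low | Exponential | 67% (Emax truth); 82-98% (other truths) |
| Low | Logistic, Sigmoid Emax | 84-95%, but 62-64% under exponential truth |
| Medium-low | Linear | 37-95% |
| Medium-low | Best AIC | 67-90% |
| High | Any single model | 94-99% |

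At the low dose the averaged estimate has a true SD of 5.1-7.4, against the linear model's SE of 3.5. At the high dose the single-model SE is about 7.0 and the SD of the averaged estimate is 6.5-6.9, so nothing is understated there.

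**An interval for the averaged curve.** A parametric bootstrap percentile interval (600 trials × 300 draws per truth, model set held at the models significant in the observed trial) covers 90-95% at the low dose, 93-96% at medium-low and 94-96% at high. Its mean half-width at the low dose is 8.2-13.5 points, against 1.96 × 3.5 = 6.9 for the linear band. At the high dose it is 12.8-13.2, against 1.96 × 7.0 = 13.7.

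**The case against.** The strongest reply is that valid uncertainty for every arm is already planned. SAP 7.4 tabulates and plots MMRM means, SEs and 95% intervals per dose and visit. It overlays the per-dose intervals on the uncorrected single-model figures, its SAS code requests pairwise differences with intervals, and the observed-case displays carry t-based intervals for differences to placebo. The model-free difference interval at the low dose covers 94-95% in simulation. All of this stands, so a reader should not infer that the SAP offers no sound uncertainty at the lower doses. But these intervals describe the raw arms, not the averaged curve or the target dose, and they are not listed for the placebo-corrected figure.

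Three further points stand:

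- The SAP already says that each band belongs to its shape, so relabelling alone would add little.
- It does not single out the best-AIC model for display. That figure shows only that picking the best fit does not cure the problem.
- Dose choice is not mechanical, since safety and other information also count.

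The R code sections that SAP 7.4 cites (9.4 and 9.4.1) are not in the public text. The documents therefore show that no interval is listed for the averaged curve, not that none will be computed.

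**Conclusion.** The point holds as a reporting gap that matters for dose selection. The averaged curve, its per-dose estimates and the target dose have no listed interval. Of the single-model bands shown in its place, the linear one is significant, and so displayed, in at least 98% of positive trials. At the low dose it covers about 7-26% under the four non-linear planned truths.

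Three stronger readings are not supported:

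- **That all the bands are far too narrow at the lower doses.** Logistic and Sigmoid Emax bands are mostly adequate there. Much of the failure elsewhere is bias from the wrong shape rather than too small an SE.
- **That proof of concept is compromised.** All candidate shapes are monotone, so the maximum benefit lies at the high dose, where single-model bands cover 94-99%. The rule uses a test and a point estimate, with no interval.
- **That the binary endpoints have a problem of the same size.** No calculation here addresses them.

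The figures assume the back-solved dose ratios, SD 35, no dropout, assumed parameter bounds and conventional AIC weights. The hand check also uses the rounded means of Table 7.5: 1 and ignores the reduction in SD from setting values to -100%.

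**What to change.** In SAP 7.4, add a parametric bootstrap. Draw Week 16 mean vectors from a normal distribution with the MMRM estimates and their covariance. In each draw repeat the MCP step, the refits and the averaging. State the weights as proportional to exp(-0.5 × AIC): the printed formula lacks the minus sign and as written would favour the worst-fitting model. Report percentile 95% intervals for the averaged curve, its difference to placebo, the maximum benefit and the target dose.

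State two rules in advance:

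- Draws in which no model is significant: for example, average over all candidates, or over the models significant in the observed data. The coverage check above used the latter set in every draw, so if the MCP step is repeated the chosen rule should be checked by simulation.
- Draws in which the target effect is never reached: report their proportion.

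Also overlay the MMRM arm-minus-placebo 95% intervals on the placebo-corrected figures. The same displays may be added to SAP 7.5.2 for consistency.

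The cost is one SAP paragraph and a few lines of R; no test, alpha level or sample size changes. Intervals at the low dose would be wider than the linear band but not wider than every single-model band: the largest median SE there, 8.7, implies a half-width of 1.96 × 8.7 = 17.1. At the high dose they would be about the same as now.

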7.5 SECONDARY ENDPOINTS

7.5.1 Key secondary endpoint

This section is not applicable as no key secondary endpoint has been specified.

7.5.2 Secondary endpoints

Continuous secondary endpoints

Continuous secondary endpoints up to week 16 will be evaluated using MMRM model and MCP-Mod in the same way as for the primary endpoint.

For percent change in PPP ASI from baseline at Week 52, a similar setting to that described for the primary endpoint MMRM model (in [Section 7.4](#)) will be applied with the inclusion of the additional visits of Week 28, 40 and 52.

Binary secondary endpoints

For each of the binary secondary endpoints at Week 16, a logistic regression and MCPMod model will be used to evaluate the treatment effect of multiple doses of Spesolimab vs. placebo. This method will be implemented for MCPMod in a binary setting.

The primary analysis of binary secondary endpoints will be based on the FAS. Any data collected after use of any rescue therapy or after 6 weeks following last drug administration if a patient discontinued treatment early will be censored as the primary estimand (EC).

Logistic regression analysis

For binary endpoints, the difference in the proportion of patients with a response between Spesolimab and placebo will be analysed, for the FAS, using a logistic regression approach with a logit link via PROC LOGISTIC in SAS[®]. Fixed classification effects will include treatment and region (Japan vs. Non-Japan). In case 0 event is observed in any of the combination of dose group and strata a penalized regression based on the Firth's bias reduction method ([19](#), [20](#)) will be used.

The estimates from the logistic regression are on the logit scale, and the difference in proportions will be calculated as the difference between the predicted probabilities in the treatment groups on the original scale. Odds ratio will be also reported between each Spesolimab arm vs placebo

Confidence intervals will be calculated using the cumulative distribution function method of Reeve (14). More specifically, as suggested in Reeve (14), a numerical search algorithm will be employed to find the quantiles x_A of the cumulative distribution function, $F_{\widehat{\Delta p}}$, such that $F_{\widehat{\Delta p}}(x_A) = A$, where $A = 2.5\%$ and $A = 97.5\%$ and $F_{\widehat{\Delta p}}$ is given by equation (10) in Reeve (14). R code that will be used to implement this is provided in [Section 9.2](#).

MCP-MOD analysis

The estimate of response rate from each dose group obtained via logistic regression or penalized regression based on the Firth's bias reduction method (as described above) without intercept will be used as basis for the MCPMod analysis of the binary secondary endpoints. The subsequent MCP-Mod analyses are based on the response rates on the logit scale.

The multiple comparison procedure will be implemented using optimal contrast tests which control the family-wise type I error rate at a one-sided $\alpha = 0.05$. The same candidate models as for the primary endpoint will be used for all secondary binary endpoints. For the MCPMod test, the optimal contrasts of each candidate model are calculated using the R-function `optCont` using weights (w) proportional to the sample size of each dose group, respectively, and are shown in [Table 7.5.2: 1](#). These contrasts will be recalculated using the actual sample size of the dose groups (in case this differs from the planned numbers). The final contrasts will be presented in the CTR.

Table 7.5.2: 1 Contrast coefficient

Model	Contrast coefficients for (total) dose				
	Placebo	Low dose: [REDACTED]	Medium-low dose: [REDACTED]	Medium-high dose: [REDACTED]	High dose: [REDACTED]
Linear	-0.783	-0.049	0.049	0.196	0.587
E _{max}	-0.869	0.112	0.151	0.190	0.416
Exponential	-0.574	-0.194	-0.118	0.106	0.780
Logistic	-0.706	-0.220	0.036	0.279	0.612
Sigmoid E _{max}	-0.638	-0.247	-0.052	0.256	0.681

BI: Spesolimab total dose, [REDACTED] administered before week 16.

The MCP-Mod test will be applied using these fixed contrasts. R code is also available in [Section 9.4.2](#).

[figure not shown]
All significant dose-response models will be re-fitted to the data without any parameter assumptions to generate a set of new estimates of the model parameters from the data. The final model is derived as a weighted average over all significant model shapes obtained via the same averaging procedure as described for the primary endpoint.

The following displays are planned.

- Table of the contrast coefficients per dose group and candidate model, together with the MCPMod test statistics and p-values for each model and the critical value
- For the average model, figure of the dose-response curve
- For all significant model shapes, figures of the dose-response curve plus 95% confidence band (of the predicted shape)

Descriptive statistics

Descriptive statistics and graphical displays (line plots) of the response on each binary endpoint will be produced using EC-NRI, OC and OC-IR methods respectively. The method to provide confidence intervals for single proportions will be based on Wilson (16). The method to provide confidence intervals for risk differences is derived from the Wilson method by Newcombe (17).

7.5.3 Analysis of % change in PPP ASI from week 16

Analysis regarding the % change in PPP ASI will be performed, using the FAS-post 16 set, which focuses on the maintenance treatment period post primary endpoint (Week 16). Data starting from the first dose administered at Week 16 will be evaluated using the MMRM model where week 16 data will be used as baseline and visits at week 28, 40 and 52 will be included. Patients who didn't receive treatment at week 16 will be excluded from this analysis.

[figure not shown]
MMRM model accounts for the following sources of variation: 'baseline' (week 16) as a continuous covariate, and 'visit', 'dose group', 'region' (stratification according to Japan vs. non-Japan), 'dose group*visit' and 'visit*baseline' (week 16) interaction as fixed effects as well as the random 'subject' effect.

[figure not shown]
In the event of model non-convergence, the methods described for the primary endpoint analysis in [Section 9.3](#) will be repeated except that ANCOVA model at week 52 and not at week 16 will be instead performed.

[figure not shown]
Dose groups will be presented per the dose regimen administered post primary endpoint (Week 16) as follows:

[figure not shown]
- [REDACTED] (i.e., Arm 4)
- [REDACTED] (i.e., Arm 2)
- [REDACTED] (i.e., Arm 1 + Arm 3 + Arm 5)

Results of the MMRM (N, adjusted mean, SE and 95% CI per dose groups and timepoint) will be presented in tables and displayed graphically. No statistical comparisons will be performed. Note that the results from this analysis need to be interpreted with caution as the efficacy outcomes post week 16 may also be impacted by treatments administered before week 16 and FAS-post 16 could not represent all population of the trial.

